6.3 Participant Discontinuation/Withdrawal from the Study

Participants may stop participating and withdraw from the study at any time. All information and data collected up until that point will be used in the study.

If a participant wishes to withdraw consent, they should contact study staff. A participant may also revoke HIPAA authorization and must provide the revocation in writing. Study staff may attempt to obtain a reason for withdrawal from the participant and record it in the study database.

In the acute pain trial, the principal investigators or clinical site investigators may withdraw a participant from the study for any of these reasons:

- Participant does not have the surgery within 12 months of study enrollment
- Participant has the surgery at a healthcare system that is different from where the participant enrolled
- Participant's surgery is scheduled for a date after the close of the enrollment period for that clinical site
- Participant is unable to have the surgery for other medical reasons

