7.3 Follow-up Participant Assessments

The event that starts the post-intervention data collection timing are as follows.

Acute Pain:

- Date of surgery (intervention and control arms)

Chronic Pain and Depression:

- Intervention arm: When the pharmacogenetics results are returned to the provider and deposited in the EMR
- Control arm: At date of DNA sample collection plus one week, where one week reflects the average time from sample collection to returning the results to the EHR
- Note: There will be variability in time the results are returned to provider and when genotype-guided therapy is delivered to the participant, time from results being available to the next provider-participant interaction (e.g. email, clinic visit, new prescription order, phone visit, etc.) will be recorded by study personnel.

Post intervention assessment collection may be done by the University of Florida College of PharmacyCall Center. The center agents will be trained survey collectors*, using an IRB approved telephone script. The collected survey responses will be entered into the study database. If preferred, the participant will have the option to complete the study follow-up survey by a URL link sent by text (to mobile phone) or email and captured in REDCap database

In the event that the call center is unable to reach a participant, local study coordinators may contact participants to facilitate completion of the follow-up surveys.

Data will be collected in the following timeframes*:

- Acute pain: 10 days, 1 month, 3 months, and 6 months post-surgery
- Chronic pain and depression: 1-month, 3 months, and 6 months post return of results for the intervention arm, and post baseline assessments for the control arm.

*See *MOP for call center agents and survey collection interval windows*

All Trials

PROMIS 43 – Adults (≥ 18 years of age) will complete a 43-question survey assessing well-being and sub domains: pain interference, physical function, sleep disturbance, social role and activities functioning, fatigue, anxiety, and depression.[32] This survey will be administered to adult participants at baseline, 1-month, 3-months, and 6-months post-surgery (acute pain), or baseline, 1-month, 3-months, and 6-months post return of results (chronic pain, depression).

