7.5 Specimen Transfer and Genetic Testing Procedures

All collected specimens will be clearly marked with two patient identifiers (CLIA requirement). Samples from the Intervention arm participants will be processed, using analytically validated PGx testing procedures (see Table 1 for gene and variant list). For Control arm samples, designated laboratories will either extract DNA after sample receipt, and store the DNA for later analysis or store the sample and extract DNA after the Control participant has completed the 6-month follow-up assessment. After the Control participant has completed the 6-month follow-up assessment, Control Arm samples will be processed using analytically validated procedures. Details of sample storage and transport will be presented in the MOP.

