7.9 Data Collection from CMS and State Medicaid Agencies

Medicare and Medicaid claims data from CMS and state Medicaid agencies will be used to assess health care utilization, costs, and medications among participants covered by either Medicare or Medicaid. Claims made in the period of 12 months prior to surgery (acute pain) or return of results (chronic pain, depression) through 6 months following those events will be collected. See Section 9 and the MOP for additional details. Schedule of Activities and Timeframe for Collection of Endpoints

Table 8. Data collection schedule

Data collection schedule, method of data collection, and timing

Outcome	Data source/instrument	Baseline	10 d ± 3 d	1 mo. ± 7 d	3 mo. ± 14 d	6 mo. ± 14 d
Pain Assessments						
Pain intensity	PROMIS Pain intensity scales	AP, CP	AP	AP, CP	AP, CP*	AP, CP
Pain intensity	PROMIS Numeric Rating Scale - Pain Intensity (NPRS)	AP	AP*	AP	AP	AP
Daily opioid dose & type of opioid use	Average daily mg morphine equivalents (MED) since discharge use of opioids: tramadol/ codeine vs others		AP*	AP		
Opioid use disorder	PROMIS - Prescription pain medication misuse subscale	AP, CP			AP, CP	AP, CP
Mobility	PROMIS mobility	AP	AP	AP	AP	AP
Depression Assessments						
Depressive state	PROMIS Emotional Distress - Depression 8b survey	CP, D		CP, D	CP, D*	CP, D
Depressive state	Patient Health Questionnaire-8 depression scale	D			D	D
Participant Medications						
Assessment of prescriptions	Custom survey/EHR	AP, CP, D	AP		CP, D	
Assessment of filled prescriptions	Medicaid and Medicare billing records for 12 months prior to time 0 through 6 months after time 0			AP, CP, D		

Adherence	Voils Medication Adherence		D		D	D	D
SSRI AE Survey	Custom survey		D		D	D	D
Opioid side effect survey	Adapted medication side effect survey (SPACE)		AP, CP	AP	AP, CP	AP, CP	AP, CP
Opioid persistence	Custom survey						AP
Participant Actions							
Interaction with provider	Participant visits				CP, D		
Interaction with test result	Custom survey						AP, CP, D
Quality of life and well being							
Past Medical History	Participant visits/custom survey		AP, CP, D				
Well-being	PROMIS43/PROMIS Peds37		AP, CP, D		AP, CP, D	AP, CP, D	AP, CP, D
Healthcare Utilization and Costs							
Medicare/Medicaid billing records	Medicaid and Medicare billing records for 12 months prior to time 0 through 6 months after time 0				AP, CP, D		
LoS	LoS for index admission			AP			

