9.2 Data Collection

Data for this specialized analysis will come from these sources:

1. Participant report of healthcare utilization (e.g. emergency department, urgent care, office) for all participants, these will focus on high-cost items and/or items that are expected to be sensitive to the intervention
2. Medicare claims data for Medicare enrollees
3. Medicaid claims data for Medicaid enrollees

Participant reported visits: Participant reported assessment for health care utilization is previously described in section 7.3.

Medicare claims data: For Medicare enrollees in fee-for-service (FFS) plans or Medicare Advantage, clinical groups will ascertain Medicare claims data (Part A-D) directly from the Centers for Medicare and Medicaid Services (CMS).

Medicaid claims data: For Medicaid enrollees, clinical groups will ascertain claims data from their states' Medicaid agencies directly.

To ensure full adjudication, requests to Medicare/Medicaid for claims data will be timed to occur between 6-12 months after the end of the 6-months follow-up of the last enrolled patient. Claims data will also be requested for one year before trial enrollment up to 6 months thereafter.

The procedure for obtaining claims data will require a database linkage step – mapping the participant study ID to the Medicare/Medicaid identifiers. The data linkage will rely on social security number (SSN) or Medicare ID and date of birth (DoB), which can be collected in two possible ways:

1. Both SSN and/or Medicare ID and DoB are collected as part of the trial by the recruiting site
2. One or both variables are extracted from the medical record of the participating health center by a healthcare data security officer or the local equivalent, on behalf of the study team

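### Section 9.2 ties the claims window to enrolment while Section 7.9 and Table 8 use surgery, return of results or time 0; in acute pain the 9.2 window loses post-surgical follow-up when surgery is late

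*Combined protocol and SAP*

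**What the plan says.** The plan describes the claims window in three ways.

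- Section 9.2: "Claims data will also be requested for one year before trial enrollment up to 6 months thereafter".
- Section 7.9, text: "12 months prior to surgery (acute pain) or return of results (chronic pain, depression) through 6 months following those events".
- Table 8, under Section 7.9, in two rows: "Medicaid and Medicare billing records for 12 months prior to time 0 through 6 months after time 0".

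Section 10.6 adds a further term. It compares overall expenditure from an *index visit*, which is not defined, to 6-month follow-up. Section 9.1 says that every economic metric covers a 6-month follow-up period, and it assumes that controls are still free of any effect of their delayed testing.

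Section 7.3 defines when follow-up starts. In acute pain it is the date of surgery in both arms. In chronic pain and depression it differs by arm: "Intervention arm: When the pharmacogenetics results are returned to the provider and deposited in the EMR" and "Control arm: At date of DNA sample collection plus one week". The week stands for the average time from sampling to results.

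Two other provisions matter. Section 6.3 lists, among the reasons for which an investigator may withdraw an acute pain participant, "Participant does not have the surgery within 12 months of study enrollment". A gap of up to 12 months is therefore allowed. Section 7.5 says of the delayed arm: "After the Control participant has completed the 6-month follow-up assessment, Control Arm samples will be processed using analytically validated procedures".

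**The concern.** The economic comparison needs claims for time 0 to month 6 in both arms. A window counted from enrolment supplies that only if time 0 comes soon after enrolment. In acute pain it need not: the window can close before the operation, and pre-operative months would then be costed as follow-up.

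The effect would spread beyond the claims totals. Section 9.2 derives extrapolation factors by pairing claims with self-reported encounters and applies them to all participants. Self-report follows the post-surgery schedule, so an enrolment window would pair different periods. The ICER in Section 10.6 would likewise set costs from one period against PROMIS-43 utilities from another. Section 9.1 cites Medicare and Medicaid shares of 53% + 4% = 57% for knee and 59% + 4% = 63% for hip arthroplasty, so claims are expected to be a main source of cost data for this kind of surgery.

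The wording in Section 7.9 raises a separate question for chronic pain and depression controls, whose results come back only after the 6-month assessment.

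**Working it through.** The plan gives no figure to reproduce. The check is how much of the follow-up interval lies inside each stated window.

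**Formula.** With follow-up from t0 to t0 + 6 months and a window from a - 12 to a + 6 around an anchor a, coverage in months is

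max(0, min(t0 + 6, a + 6) - max(t0, a - 12)).

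**Which dates differ.** In acute pain, surgery is time 0, so there are two distinct anchors: enrolment and surgery. In the chronic pain and depression intervention arms, return of results is time 0, so again there are two. Only chronic pain and depression controls can have three: enrolment, DNA collection plus one week, and actual return of results.

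**Acute pain, Section 9.2 window.** Put enrolment at 0, so a = 0 and t0 = s. Coverage reduces to max(0, 6 - s).

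| s, months from enrolment to surgery | Post-surgical months covered | Share of 6 |
|---|---|---|
| 0 | 6 | 100% |
| 1 | 5 | 83% |
| 3 | 3 | 50% |
| 5 | 1 | 17% |
| 6 to 12 | 0 | 0% |

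The synopsis gives participation as up to one year from consent to end of follow-up. Taken strictly, s + 6 ≤ 12, so s ≤ 6; surgery at month 6 meets that limit and still has no coverage. Surgery at month 12 plus 6 months of follow-up would take 18 months, so Section 6.3 and the synopsis do not agree either.

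**Chronic pain and depression, Section 9.2 window.** Again a = 0, and coverage is 6 minus the gap from enrolment to time 0. The documents give no distribution for this gap, so I assume a range (30.4375 days per month).

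- Controls, DNA taken g days after enrolment, gap (g + 7)/30.4375 months: 96% at g = 0, 92% at 7, 80% at 30, 63% at 60.
- Intervention, results returned r days after enrolment, gap r/30.4375 months: 96% at r = 7, 84% at 30, 67% at 60.

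**Chronic pain and depression controls, Section 7.9 read literally.** Put time 0 at 0 and actual return at R months, so a = R. The timing of R is an assumption; Section 7.5 implies about 6 or more.

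- Whole window: coverage is 6 - max(0, R - 12), not below 0. That is 6 of 6 for R up to 12, 5 of 6 (83%) at R = 13, 3 of 6 (50%) at R = 15, and 0 at R = 18.
- Segment after return: coverage is max(0, 6 - R). That is 0 at R = 6. If the 6-month assessment is 14 days early (the Table 8 limit) and results return at once, it is 14/30.4375 = 0.46 months, or 8%.
- Look-back before time 0: max(0, 12 - R), which is 6 months at R = 6 instead of 12.

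**Table 8 window.** Here a = t0, so coverage is 6 of 6 months with a 12-month look-back in every trial and arm.

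**The case against.** The strongest reply is that this is loose wording and not a defect in the analysis. The Section 9.2 sentence concerns a data request and says that claims will *also* be requested. The same section describes 2020-2024 Medicare and Medicaid data for trial participants, so capture may be wider than the sentence suggests. Section 9.1 already fixes a 6-month follow-up period. The 12-month surgery limit is an optional withdrawal criterion, no distribution of surgery dates is given, and self-reported utilisation is collected after surgery whatever the claims window. Further detail is deferred to the MOP and to separate analysis plans.

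Part of this stands. The documents do not show that capture is limited to the enrolment window, and the table above shows what the rule does at given values of s, not an expected loss. But the sentence is the only participant-level window in Section 9.2, and nothing says which anchor governs. Wide capture does not define the costing period either, and the *index visit* in Section 10.6 does not settle it.

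A reader might go further and infer that the claims windows miss the randomised follow-up of all chronic pain and depression controls. The documents do not support that. The enrolment anchor costs those controls only the gap to time 0. The Section 7.9 window, even read literally, contains their whole follow-up if results return within 12 months of time 0. The literal reading is also unlikely: Sections 3.1, 7.3 and 10.7 use time since return of results as a label for follow-up in both arms, Section 7.3 gives controls a nominal date, and Table 8 says time 0 outright. What remains is an ambiguity. Taken literally, it would put controls' follow-up in the prior segment, shorten their look-back to about 6 months, and make the post-period post-testing time in one arm only, against the assumption in Section 9.1.

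**Conclusion.** The anchors conflict, and the Section 9.2 rule is wrong as written for acute pain. Followed literally, it covers max(0, 6 - s) of the 6 post-surgical months: half at 3 months from enrolment to surgery, none from 6 months on. How many participants this touches cannot be derived from the documents. The loss should be similar in the two arms if time to surgery is, so the likelier harm is lost or diluted cost information, not a bias towards one arm.

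For chronic pain and depression, the enrolment anchor has a smaller effect, between 4% and 37% of follow-up over the assumed gaps of one week to about two months. The Section 7.9 wording needs clarifying for controls but probably means time 0.

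The consequence is confined to cost, utilisation and ICER analyses. Healthcare utilisation is a stated objective and Section 2.1 mentions economic impact among secondary analyses, but the synopsis calls these analyses exploratory and Section 3.2 lists no cost endpoint. No primary or secondary endpoint depends on the window.

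**What to change.** State one claims window in Sections 7.9, 9.2 and 10.6: from 12 months before to 6 months after time 0, as defined in Section 7.3 and already used in Table 8. Replace *index visit* in Section 10.6 with time 0. Set the date range of the data request wide enough to cover that window for every participant, including those with late surgery.

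While doing so, reconcile two related statements: Section 7.3 also times control follow-up from the baseline assessments, and the one-year participation limit in the synopsis does not fit the interval to surgery in Section 6.3.

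The cost is wording and a date range. Section 9.2 schedules the requests for 6 to 12 months after the last participant's 6-month follow-up ends, so the change can be made before they are sent. It adds no participant burden and leaves the primary analysis as it is.

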10. STATISTICAL ANALYSIS PLAN AND SAMPLE SIZE

10.1 Sample Size Determination

All trials power analyses are based on a modified intent to treat analysis, comparing the subset of intervention participants with have an actionable phenotype to the subset of control participants with an actionable phenotype. Effect sizes used to estimate power are based on prior studies of pain and depression pharmacogenetic testing and described below for each trial and shown in Table 8. Several steps were taken to generate a conservative sample size estimate. First, the power requirement was set to 90%. Second, sample sizes are adjusted for a 10% drop-out (for which UF has data from several studies that this is a good estimate). Third, slightly smaller effect sizes than what was observed in prior studies was used. Finally, sample size calculations are based on an alpha of 0.049, to allow one interim analysis with an alpha of 0.001 in each study.

Due to the study design and the delay in the control arm to obtaining the genotyping results required determine the actionable phenotype subgroup assignment, it is not feasible to directly monitor the number of randomized participants in the actionable subgroup for the enrollment stopping rule. Alternatively, the observed trial specific actionable phenotype percentages and the corresponding trial specific total enrollment targets will be used to identify when enrollment can conclude for a fully powered mITT study.

Acute Pain

In the University of Florida's pilot acute pain study, the difference between study arms in SIA score was -38.55 with a SD of 93.5, for a standardized effect size of 0.412. Assuming a reduced standardized effect size of 0.375, 304 participants with an actionable phenotype per group, 152 from the intervention arm and 152 from control arm, are required to achieve 90% power for a two-sided two-sample t-test. Preliminary data from the University of Florida's acute pain study indicates the proportion of participants with an actionable phenotype, genotypic or pheno-converted CYP2D6 IM or PM, will be approximately 18%. After adjusting for the subset anticipated to have an actionable phenotype, 845 participants completing all assessments, per group, are required to achieve 90% power in the sub-group analysis (1678 total). Assuming 10% drop out or lost to follow-up and 7% of participants not going on to surgery, a total of 2020 randomized participants is required to sufficiently power this study. Factoring in variability in the proportion that are IMs or PMs (15% to 24%), 1516 to 2424 randomized subjects would be need to achieve 90% power in the mITT analysis.

Chronic Pain: In the University of Florida's prior chronic pain study, the difference between study arms in composite pain score was 0.6 with a SD of 1.4, for a standardized effect size of 0.43. The same effect size was observed when assessing 3-month changes in pain scores. Assuming a standardized effect size of 0.40, 268 participants within the specified subgroup, 134 from the intervention arm and 134 from control arm, are required to achieve 90% power for a two-sided two-sample t-test. Preliminary data indicate the proportion of participants with an actionable phenotype will be 30-35%; 10-15% of participants with an actionable genotype-based phenotype (CYP2D6 IM or PM) and an additional 20% with a pheno-converted PM/IM based on drug-drug-gene interactions. After adjusting for the subset anticipated to have an actionable phenotype, 447 participants completing all assessments, per group, are required to achieve 90% power in the sub-group analysis (894 total). Assuming 10% drop out or lost to follow-up, a total of 994 randomized participants is required to sufficiently power this study. Factoring in variability of the proportion of randomized population that are IMs or PMs (24-33%), 906 to 1244 randomized subjects would be need to achieve 90% power in the mITT analysis.

Depression:

In prior studies of depression, the difference between study arms in PROMIS 8a T-scores was -6.7 with a SD of 10, for a standardized effect size of -.67. For the purposes of power analysis, a 4-point change is considered the minimally important difference representing a response to therapy that is congruent with the predicted CYP enzyme phenotype compared to the response to therapy which

conflicts with the phenotype.

Preliminary data from published studies indicate the proportion of participants with an actionable phenotype (CYP2C19 PM, RM, UM or CYP2D6 PM or UM, or pheno-converted CYP2D6 PM or UM) will be 40%. However, due to the distribution of study-related antidepressants in primary care and behavioral health settings, an estimated 67% of the participants with an actionable phenotype are anticipated to also have a study-related dosing or drug selection intervention. In other words, the analytic group of CYP2DC UM, PM, or CYP2C19 UM, RM, or PM phenotypes will represent a mixture of participants that may have a clinically meaningful change in depression due to being prescribed a study-relevant antidepressant and participants that may have changes in depression typical of the standard of care arm since they are not being prescribed a study-relevant antidepressant. In accounting for this population mixture, we incorporated a dilution factor of 67% into the clinically meaningful effect size projection and assume the effective difference of 0.28, representing a 2.8-point change to the T-score. We will need 542 modified intent to treat participants, 271 in each arm, to detect a standardized effect size of 0.28 with 90% power. After adjusting for the subset anticipated to have an actionable phenotype (i.e. 40%), 678 participants completing all assessments, per group, are required to achieve 90% power in the mITT analysis (1356 total). After accounting for 90% retention, 754 participants from the intervention arm and 754 participants from control arm (1508 total) are required to achieve 90% power for a two-sided two-sample t-test. Factoring in variability for the on the mITT proportion of the randomized population (40-60%), 1006-1508 randomized subjects would be needed to achieve 90% power in the mITT analysis.

Table 9. Sample size calculations

Sample size calculations for each trial, assuming an alpha of 0.049 to allow for one interim analysis

Study	Assumed Actionable Phenotype	Total N	Completed N (90% assumed)	Intervention	Usual Care	Intervention: Actionable Phenotype	Usual Care: Actionable Phenotype	Effect Size	Power
Acute Pain (CYP2D6 IM/PM)	18% (15%-24%)	2,020 (2424-1516)	1,690* (2028 - 1268)	845 (1014 - 634)	845 (1014 - 634)	152	152	0.375	90.00%
Chronic Pain (CYP2D6)	30% (24% - 33%)	994 (906 - 1244)	894 (814-1118)	447 (407-559)	447 (407-559)	134	134	0.4	90.00%
IM/PM)									
Depression (CYP2D6 or CYP2C19 PM/UM)	40% (up to 60%)	1,508 (1006)	1,356 (904)	678 (452)	678 (452)	271	271	0.28	90.00%
Total		4,522	3,940	1,970	1,970	557	557		

*Accounts for an additional 7% of participants not completing surgery

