	
metabolizers (IM), there was greater improvement in pain control in the genotype-guided arm compared to usual care arm[1]. Similarly, existing studies of PGx tailored antidepressant therapy suggest that the genotype-guided approach is superior to usual care in remission and/or response rates, however these studies are small and often industry-sponsored.
 
A broader trial is needed to determine the importance of PGx testing and genotype guided therapy for improving symptom management (i.e. pain control or control of depression symptoms), DEA schedule II opioid use, well-being, and overall healthcare utilization.

Study Population	
Acute Pain Randomized Population Approximately 1730* participants with planned/elective surgery who are anticipated to start a paincontrol medication with existing CPIC guidelines after their surgery
 
Analytical Population Approximately 304 participants from the randomized population who have an actionable phenotype defined as CYP2D6 IM or PM (i.e. CYP2D6 activity score ≤ 0.75)
 
Chronic Pain Randomized Population Approximately 985* participants see in primary care or pain specialty clinics who are already prescribed or anticipated to be prescribed tramadol, codeine, or hydrocodone for pain control.
 
Analytical Population Approximately 268 participants from the randomized population who have an actionable phenotype defined as CYP2D6 IM or PM (i.e. CYP2D6 activity score ≤ 0.75)
 
Depression Randomized Population Approximately 1540* participants seen in primary care or psychiatry clinics who are already prescribed or anticipate to be prescribed an SSRI with existing CPIC guidelines
 
Analytical Population Approximately 542 participants from the randomized population who have an actionable phenotype, defined as a CYP2D6 PM or ultra-rapid metabolizer (UM), or a CYP2C19 PM, rapid metabolizer (RM), or UM

	*Subject to change based on the actionable phenotype rates and missing data.
Number of Sites	11 sites with approximately 60-80 clinics
Duration of Subject Participation:	Up to one year from consent to end of follow-up

Description of implementation of intervention (e.g.,	The intervention for ADOPT PGx is the immediate return of PGx testing results to the participant's healthcare provider.

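### Depression sample size: 4 points × 67% at SD 10 gives 0.268, not 0.28, and at 0.268 the planned 271 per arm has 87% power, not 90%

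*Combined protocol and SAP*

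**What the plan says.** The depression part of section 10.1 (Sample Size Determination) builds its effect size in three steps.

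- It reports an SD of 10 T-score points from prior studies, and for the power analysis "a 4-point change is considered the minimally important difference".
- It expects only 67% of participants with an actionable phenotype to be on a drug for which the testing would alter choice or dose. The others are expected to change as under standard care.
- To allow for that mixture, "we incorporated a dilution factor of 67% into the clinically meaningful effect size projection and assume the effective difference of 0.28". The same sentence translates 0.28 into 2.8 T-score points.

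The stated requirement is then 542 analysed participants, "271 in each arm, to detect a standardized effect size of 0.28 with 90% power". Dividing by 40% actionable and 90% retention leads to 678 completers and 754 randomised per arm, 1508 in all. On the error rate, "sample size calculations are based on an alpha of 0.049, to allow one interim analysis with an alpha of 0.001 in each study". The depression row of Table 9 repeats 271 per arm, 0.28 and 90.00%. The Protocol Synopsis gives a slightly larger randomised target: "Approximately 1540* participants seen in primary care or psychiatry clinics".

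**The concern.** The inputs and the result stand in one paragraph and disagree. If 67% of the analysed group can gain 4 points and the rest gain nothing, the average gain is 2.68 points, not 2.8. The step that produces 0.28 is therefore either an arithmetic slip or rests on an input that is not stated.

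This matters because 0.28 is the only effect assumption behind the depression sample size. It determines 271, 542, 678, 1356 and 1508, and also the lower figure of 1006 at 60% actionable. Section 10.1 explains that the number of actionable participants cannot be monitored directly, so the observed actionable percentages and the matching enrolment targets decide when enrolment may close with the study considered fully powered. It also describes the estimate as conservative, whereas this discrepancy runs the other way. A reader weighing a null depression result would take the miss rate for the diluted difference to be 10%, when on the stated inputs it is larger.

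**Working it through.** **Inputs, all from section 10.1:** clinically meaningful difference 4 points; SD 10; dilution factor 67%; two-sided alpha 0.049; two-sample t-test; power 90%; 40% actionable; 90% retention. Arms are equal.

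**Method.** Power is the probability that a noncentral t variable with 2n − 2 degrees of freedom and noncentrality d × √(n/2) falls outside the two-sided critical values, where d is the standardised difference and n the number per arm.

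**1. The plan's own figure reproduces.** At d = 0.28 the required n is 270.4, rounded up to 271. Power at 271 per arm is 90.06%. Downstream, 271 / 0.40 = 677.5, so 678; 678 / 0.90 = 753.3, so 754; 2 × 754 = 1508. Everything after 0.28 is correct.

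**2. The step before it does not.**

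- 4 × 0.67 = 2.68 points; 2.68 / 10 = 0.268.
- To reach 2.8 points from 4, the factor must be 2.8 / 4 = 0.70.
- To reach 2.8 points with 67%, the start must be 2.8 / 0.67 = 4.18 points.
- To get 0.28 from 2.68 points, the SD must be 2.68 / 0.28 = 9.57, but the plan equates 0.28 with 2.8 points, which fixes the SD at 10.

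**3. Power at the value the inputs give (alpha 0.049).**

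| Per arm | d | Power |
|---|---|---|
| 271 | 0.28 | 90.06% |
| 271 | 0.268 | 87.40% |
| 271 | 0.27 (0.268 rounded) | 87.87% |
| 277 | 0.268 | 88.1% |
| 271 | 0.40 (undiluted 4 points) | 99.63% |

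The 277 per arm comes from the synopsis target: 1540 × 0.40 × 0.90 = 554, or 277 per arm.

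**4. Size needed for 90% at 0.268.** n = 295.1, so 296 per arm, 592 in total: 25 more per arm, and 25 / 271 = 9%. At 40% actionable, 296 / 0.40 = 740 completers per arm; 740 / 0.90 = 822.2, so 823 randomised per arm, 1646 in total, against 1508.

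**5. Sensitivity.** If 67% is itself rounded, 66.5% to 67.5% gives d = 0.266 to 0.270 and power of 86.9% to 87.9%. Using alpha 0.05 instead of 0.049 gives 87.6% at 0.268. Neither reaches 90%.

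**6. Actionable rate that would make up the shortfall, if enrolment stays fixed.** 592 / (1508 × 0.90) = 43.6%; 592 / (1540 × 0.90) = 42.7%.

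**The case against.** The strongest reply is that the plan claims 90% power only at 0.28, and that claim reproduces exactly. This is right. The fault is confined to the link from 4 points and 67% to 0.28, and the criticism should go no further than that.

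A second reply is that the 4 points may be a rounded figure: 4.2 × 0.67 = 2.81 points, or 0.281. That could be the true origin, and section 10.2 places detailed analysis plans in separate documents that are not available here. But these documents state neither 4.2 points nor a 70% factor, so the reply explains how the gap might have arisen without closing it. It is a good reason to accept a stated derivation of 0.28 as an alternative to changing the number.

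A third reply is that the practical effect is slight. The gap is 0.12 T-score points. The prior-study difference of 6.7 points, diluted by 67%, would be 0.449 SD, for which 271 per arm has 99.9% power. An actionable rate of about 43%, near the bottom of the plan's 40–60% range, would restore 90%. All of this limits the weight of the point. The last part, however, holds only if enrolment stays at 1508 or 1540. The plan's target falls as the actionable rate rises: 1006 × 0.60 × 0.90 = 543 analysable, which is again about 271 per arm and 87% power at 0.268.

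**Conclusion.** The point holds. On the stated 4 points, SD 10 and 67%, the diluted difference is 0.268 SD. With 271 per arm, the chance of missing it is 12.6%, not 10%. At the synopsis target of 1540, with 40% actionable and 90% retained, power is 88.1%, so the larger target narrows the gap without closing it.

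This rests on equal arms, the two-sample t-test at two-sided alpha 0.049, an SD of 10 for the change score, and reading the dilution factor as a simple multiplier, which is how the plan's mixture argument describes it. The consequence is modest. The type I error, the endpoint and the analysis are unaffected, and power for an undiluted 4-point difference remains above 99%. It should still be corrected, because the effect size and the power figure are both relied on and do not follow from the inputs given beside them.

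**What to change.** In the depression part of section 10.1 and the depression row of Table 9, do one of the following:

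- restate the effective difference as 2.68 points (0.268 SD), and the power as about 87% at 542 analysed participants; or
- keep 0.28, and state and justify the input that yields it, such as a 70% factor or a starting difference of about 4.2 points.

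Under the first option, the text on when enrolment may close should use the same power figure, so that 1508 and 1006 are not described as giving 90% for the diluted 4-point difference.

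The cost is a few sentences and one table row. No additional participants are requested and no procedure changes. Under the first option the reported depression power becomes slightly less favourable.
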